3.5.5 Long-Term Safety

The incidence of AEs recorded 30 days after last treatment taken will be summarized and will display number of patients with at least one AE by SOC/PT, for the following AE:

- SAEs
- AESIs

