- b. Response will be assessed by the investigator using RECIST v1.1 (see [Appendix 2](#)) and modified RECIST (see [Appendix 3](#)). Patients who continue atezolizumab treatment beyond radiographic disease progression assessed per RECIST v1.1 will be monitored with a follow-up scan at the next scheduled tumor assessment when the scan frequency is every 6 weeks, and will be assessed by modified RECIST criteria (see [Appendix 3](#)) until treatment discontinuation. If the scan frequency is every 9 weeks (see [Appendix 1](#)), a follow-up scan is recommended at 9 weeks or earlier if clinically indicated.
- c. In those patients for whom tumor assessments are performed as part of local clinical practice and are available for report after PD or atezolizumab treatment discontinuation, best overall response (BOR) and PFS will be assessed from the first date of the new anticancer therapy to the end of the study per RECIST v1.1 and modified RECIST.

The primary objective of the study is to evaluate the long-term safety of atezolizumab. Long-term safety will be assessed by monitoring the nature, severity, duration, frequency and timing of atezolizumab-related SAEs and atezolizumab-related irAEs. An irAE is defined as any adverse event of special interest (AESI) associated with systemic corticosteroid use within 30 days of the onset date. All-causality AEs, all-causality SAEs, AEs and SAEs leading to atezolizumab interruption or discontinuation, and AESIs will also be reported, as well as causes of death, vital signs, physical findings and clinical laboratory results.

Secondary objectives will assess the efficacy of atezolizumab. The main efficacy objective will be to evaluate the OS rate 2 years after the first dose of atezolizumab.

Other efficacy objectives will include evaluation of OS, OS rate at 3 years, PFS, ORR, and DOR (additional efficacy assessments may occur on an exploratory basis). All antitumor response assessments will be based on RECIST v1.1 and modified RECIST.

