5. ASSESSMENT OF SAFETY

5.1 SAFETY PLAN

The safety plan for patients in this study is derived from clinical experience with atezolizumab in completed and ongoing studies. The anticipated important safety risks are outlined below (see Section 5.1.1).

Measures will be taken to ensure the safety of patients participating in this study, including the use of carefully chosen inclusion and exclusion criteria and close monitoring of patients during the study. Administration of atezolizumab will be performed in a monitored setting in which there is immediate access to trained personnel and adequate equipment and medicine to manage potentially serious reactions.

After initiation of study treatment, all adverse events will be reported until 30 days after the last dose of study treatment or until initiation of new anti-cancer therapy, whichever occurs first. SAEs and adverse events of special interest will continue to be reported until 90 days after the last dose of study treatment or until initiation of new anti-cancer therapy, whichever occurs first.

Guidelines for managing anticipated adverse events, including criteria for dosage modification and treatment interruption or discontinuation, are provided below (Section 5.1.2), in [Appendix 9](#) and in the Atezolizumab Investigator's Brochure. Refer to Sections 5.2–5.6 for details on safety reporting during the study.

Patients with active infection are excluded from study participation. In the setting of a pandemic or epidemic, screening for active infections (including SARS-CoV-2) prior to and during study participation should be considered according to local or institutional guidelines or guidelines of applicable professional societies (e.g., American Society of Clinical Oncology or European Society for Medical Oncology).

Severe COVID-19 appears to be associated with a CRS involving the inflammatory cytokines IL-6, IL-10, IL-2, and IFN- γ (86). If a patient develops suspected CRS during the study, a differential diagnosis should include COVID-19, which should be confirmed or refuted through assessment of exposure history, appropriate laboratory testing, and clinical or radiologic evaluations per investigator judgment. If a diagnosis of COVID-19 is confirmed, the disease should be managed as per local or institutional guidelines.

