5.4.2.2 Events That Occur after Study Drug Initiation

After initiation of study drug, all adverse events will be reported until 30 days after the last dose of study drug and until 90 days for serious adverse events or adverse events of special interest. Investigators should record all case details that can be gathered immediately (i.e., within 24 hours after learning of the event) on the Adverse Event eCRF and submit the report via the electronic data capture (EDC) system. A report will be generated and sent to Roche Safety Risk Management by the EDC system.

In the event that the EDC system is unavailable, the paper Clinical Trial Serious Adverse Event/Adverse Event of Special Interest Reporting Form provided to investigators should be completed and submitted to the Sponsor or its designee immediately (i.e., no more than 24 hours after learning of the event), either by faxing or by scanning and emailing the form using the fax number or email address provided to investigators. Once the EDC system is available, all information will need to be entered and submitted via the EDC system.

Instructions for reporting serious adverse events that occur > 30 days after the last dose of study treatment are provided in Section [5.6](#).

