5.6 ADVERSE EVENTS THAT OCCUR AFTER THE ADVERSE EVENT REPORTING PERIOD

After the end of the adverse event reporting period (defined as 30 days after the last dose of study drug for all AEs and 90 days for serious adverse events and adverse events of special interest), all deaths, regardless of cause, should be reported through use of the Long-Term Survival Follow-Up eCRF.

In addition, if the investigator becomes aware of a serious adverse event that is believed to be related to prior exposure to study drug, the event should be reported through use of the Adverse Event eCRF. However, if the EDC system is not available, the investigator should report these events directly to the Sponsor or its designee, either by faxing or by scanning and emailing the paper Clinical Trial Serious Adverse Event/Adverse Event of Special Interest Reporting Form using the fax number or email address provided to investigators.

5.7 EXPEDITED REPORTING TO HEALTH AUTHORITIES, INVESTIGATORS, INSTITUTIONAL REVIEW BOARDS, AND ETHICS COMMITTEES

The Sponsor will promptly evaluate all serious adverse events and adverse events of special interest against cumulative product experience to identify and expeditiously communicate possible new safety findings to investigators, IRBs, ECs, and applicable health authorities based on applicable legislation.

To determine reporting requirements for single adverse event cases, the Sponsor will assess the expectedness of these events using the following reference document:

- **Atezolizumab Investigator's Brochure**

The Sponsor will compare the severity of each event and the cumulative event frequency reported for the study with the severity and frequency reported in the applicable reference document.

Reporting requirements will also be based on the investigator's assessment of causality and seriousness, with allowance for upgrading by the Sponsor as needed.

An IDMC will monitor the incidence of the above-listed anticipated events during the study. An aggregate report of any clinically relevant imbalances that do not favor the test product will be submitted to health authorities.

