- r. If available, pre-treatment FFPE tumor tissue (most recent sample) for PD-L1 testing and exploratory biomarkers. Most recent archival sample or a sample obtained during screening should be submitted if available (1 FFPE tissue block or 5–10 slides).
- s. From patients who received anti-PD-1 therapy, sites are highly encouraged to provide archival FFPE tissue (prior anti-PD1 therapy) and an FFPE tissue biopsy obtained during screening (archival and screening tissue sample).
- t. Ten milliliters (10 mL) whole blood for plasma. Not applicable for a site that has not been granted approval for RBR sampling. Performed only for patients at participating sites who have provided written informed consent to participate.
- u. Only to be shipped if the patient is eligible for enrollment.
- v. See [Appendix 4](#).
- w. Concomitant medications include any prescription medications or over-the-counter medications. At screening, any medications the patient has used within the 7 days prior to the screening visit should be documented. At subsequent visits, changes to current medications or medications used since the last documentation of medications will be recorded.
- x. After informed consent has been obtained, but prior to initiation of study drug, only SAEs caused by a protocol-mandated intervention should be reported. After initiation of study drug, all SAEs and AESIs, regardless of relationship to study drug, will be reported until 90 days after the last dose of study drug or initiation of new anti-cancer therapy, whichever occurs first. All other AEs, regardless of relationship to study drug, will be reported until 30 days after the last dose of study drug or initiation of new anti-cancer therapy, whichever occurs first. After this period, the investigator should report any SAEs or AESIs believed to be related to prior study drug treatment. The investigator should follow each AE until the event has resolved to baseline grade or better, the event is assessed as stable by the investigator, the patient is lost to follow-up, or the patient withdraws consent. Every effort should be made to follow all SAEs considered to be related to study drug or study-related procedures until a final outcome can be reported.

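### The SAP 3.5.5 long-term safety table adds all-cause SAEs and AESIs from a short post-treatment window to related-only events afterwards, so its percentages are neither all-cause nor drug-related incidence

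*SAP*

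**What the plan says.** **The table.** SAP 3.5.5 reads: "The incidence of AEs recorded 30 days after last treatment taken will be summarized". The output "will display number of patients with at least one AE by SOC/PT, for the following AE" types: SAEs and AESIs. It sets no relatedness condition, no end to the window and no division of the window. SAP 3.5.2 and 3.5.3 say so explicitly when only treatment-related events are meant, so I read 3.5.5 as all-causality. I also read its window as starting more than 30 days after the last dose, which is the natural sense under that heading.

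**The collection rule.** Protocol Appendix 1, note x, says that "all SAEs and AESIs, regardless of relationship to study drug, will be reported until 90 days after the last dose of study drug", ending sooner if new anti-cancer therapy starts. Protocol 5.1 sets the same limit: "or until initiation of new anti-cancer therapy, whichever occurs first". Note x then continues: "After this period, the investigator should report any SAEs or AESIs believed to be related to prior study drug treatment". The schedule reproduced in SAP Appendix 2 carries the same note.

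**Related text that differs.** Protocol 5.6 is narrower for the later period. It asks for a report "if the investigator becomes aware of a serious adverse event that is believed to be related to prior exposure to study drug" and does not mention non-serious AESIs. Protocol 5.4.2.2 sets 90 days for SAEs and AESIs, but closes with "Instructions for reporting serious adverse events that occur > 30 days after the last dose of study treatment are provided in Section" 5.6. Sections 5.3.1, 5.4.2.2 and 5.6 do not mention the new-therapy limit.

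**The objective.** Protocol 3.1 says: "Long-term safety will be assessed by monitoring the nature, severity, duration, frequency and timing of atezolizumab-related SAEs and atezolizumab-related irAEs". The same paragraph also calls for all-causality SAEs and AESIs to be reported.

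**The concern.** The table's window runs across a change in what is collected. Up to the close of the all-causality period, an unrelated SAE enters the database and is counted. After that point an identical event is not collected, and only events judged related can appear. A reader who takes the row as all-cause late incidence will read it too low. A reader who takes it as late drug toxicity will read it too high.

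Two further effects follow. The switch point differs between patients, because new anti-cancer therapy can bring it forward. The mix also shifts as follow-up lengthens, so the primary analysis (about 6 months after the last enrolment) and the final analysis (up to 30 months after it) could show different percentages and a different SOC/PT profile for that reason alone. Terms usually judged unrelated can enter only in the early part of the window.

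What is at stake is whether a descriptive table headed Long-Term Safety, in a trial whose primary objective is long-term safety, can be interpreted.

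**Working it through.** The plan states no figure for this table, so there is nothing to reproduce. The check is one of logic, followed by an illustration on assumed values.

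**Step 1: what each period contributes**

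| Time after last dose | Collected (Appendix 1 note x; Protocol 5.1) | Counted in SAP 3.5.5 |
|---|---|---|
| Day 31 to day 90, or new therapy if earlier | All SAEs and AESIs | All-cause events |
| Later follow-up | Events believed related | Related events only |

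**Step 2: bounds that need no rate model.** Suppose related events are fully reported throughout. Every patient with a related event after day 30 is then in the row, and every patient in the row had some event after day 30. So related incidence ≤ row ≤ all-cause incidence.

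- The row equals all-cause incidence only if it loses no patient whose sole late events were unrelated and fell after the window closed. That is so if follow-up ends with the window or all later events are related.
- It equals related incidence only if it gains no patient solely through unrelated events inside the window.
- For a patient who starts new therapy by day 30 the all-causality window is empty, and only related events can count.
- If late related events are missed, even the lower bound can fail.

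**Step 3: illustration.** The documents give no post-treatment event rates. These inputs are assumptions: constant hazard λ of a first event of 0.02 or 0.05 per month; related share f of 0.1 or 0.3; follow-up F of 6, 12 or 24 months after the last dose; switch at day 90 for everyone. With 30.4375 days per month, w = 60/30.4375 = 1.971 months and T = F − 30/30.4375.

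- All-cause = 1 − exp(−λT)
- Related = 1 − exp(−fλT)
- Row = 1 − exp(−λ[w + f(T − w)])

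Worked case, λ = 0.02, f = 0.1, F = 12: T = 11.014. All-cause = 1 − exp(−0.2203) = 19.8%. Related = 1 − exp(−0.0220) = 2.2%. Row = 1 − exp(−0.02 × [1.971 + 0.1 × 9.043]) = 1 − exp(−0.0575) = 5.6%.

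Each cell shows all-cause / row / related (%):

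| λ, f | F = 6 | F = 12 | F = 24 |
|---|---|---|---|
| 0.02, 0.1 | 9.5 / 4.4 / 1.0 | 19.8 / 5.6 / 2.2 | 36.9 / 7.8 / 4.5 |
| 0.02, 0.3 | 9.5 / 5.6 / 3.0 | 19.8 / 8.9 / 6.4 | 36.9 / 15.3 / 12.9 |
| 0.05, 0.1 | 22.2 / 10.8 / 2.5 | 42.3 / 13.4 / 5.4 | 68.4 / 18.4 / 10.9 |
| 0.05, 0.3 | 22.2 / 13.4 / 7.2 | 42.3 / 20.9 / 15.2 | 68.4 / 33.9 / 29.2 |

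The smallest and largest shortfalls from all-cause are 9.5 − 5.6 = 3.9 and 68.4 − 18.4 = 50.0 points. The smallest and largest excesses over related are 15.3 − 12.9 = 2.4 and 10.8 − 2.5 = 8.3 points.

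The related share of expected events counted is fT/[w + f(T − w)]. At 6, 12 and 24 months it is 22%, 38% and 56% for f = 0.1, and 52%, 71% and 83% for f = 0.3. The composition changes with follow-up even though the underlying rates do not.

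**The case against.** The strongest reply is that this is a supplementary descriptive table and the primary endpoints sit elsewhere. That stands. SAP 3.5.2 analyses drug-related SAEs and drug-related irAEs with exact confidence intervals, and SAP 3.5.4 and 3.5.6 cover irAE timing and duration.

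A reader might infer from the heading that the SAP has replaced the protocol's related-event measure of long-term safety with an all-causality one. The documents do not support that. The related-event endpoints are in 3.5.2, and Protocol 3.1 itself asks for all-causality SAEs and AESIs as well.

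A reader might also fault the table for having no irAE row. That does not hold either. Protocol 3.1 defines an irAE as an AESI with systemic corticosteroid use within 30 days of onset. Protocol 4.4 records concomitant medication only up to the treatment discontinuation visit, which is at most 30 days after the last dose, and Appendix 1 has no follow-up entry for it. Late irAE status could not be derived reliably, so AESIs are the safer category.

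Finally, it is tempting to size the error from the POPLAR figures in Protocol 1.2.2.2 (41% any-cause against 12% treatment-related). Those are proportions of patients with Grade 3–4 events in another trial. They are neither SAEs nor post-treatment rates.

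None of this removes the change of collection rule inside the 3.5.5 window.

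**Conclusion.** The point holds, confined to SAP 3.5.5. Followed as written, each row pools all-cause events from a short window that varies by patient with related-only events from later follow-up. The result estimates neither all-cause nor related late incidence, and it drifts with follow-up length.

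The conclusion rests on reading 3.5.5 as all-causality and as starting after day 30, and on the collection rule in Protocol 5.1 and Appendix 1. The bounds also assume complete reporting of late related events, which the wording of Protocol 5.6 does not secure. The size is unknown: the ranges above come from assumed rates and show direction only. No primary endpoint or its interval changes. The correction is worth making because it is cheap and makes each row interpretable.

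**What to change.** **First, reconcile the collection rules in the protocol.** Sections 5.3.1, 5.4.2.2 and 5.6 omit the new-therapy limit that 5.1 and Appendix 1 contain. Section 5.4.2.2 sends SAEs after day 30 to Section 5.6 while setting 90 days itself. Section 5.6 omits the non-serious related AESIs that Appendix 1 includes. The window cannot be programmed until these agree.

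**Then amend SAP 3.5.5** to give two separate sets of rows:

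- (a) All-causality SAEs and AESIs from day 31 to day 90 or the start of new anti-cancer therapy, whichever is first.
- (b) Atezolizumab-related SAEs and atezolizumab-related AESIs (not irAEs) over all follow-up after day 30, footnoted that reporting after the all-causality window is passive and may be incomplete.

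State also whether events are placed by onset date, since the present wording refers to when they were recorded.

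**Cost.** SAP wording and one re-cut table, using the yes/no causality assessment already recorded for each event (Protocol 5.3.4). The all-cause figure will cover a shorter period, and the protocol text needs the clarification above.

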3.5.6 Duration of AEs

The time to resolution of specific AEs (in months) for AESI and irAE by Category will be analyzed and summarized using Kaplan Meier methodology.

- The start date will be the onset date recorded
- If AE is ongoing (no end-date), then the end date will be imputed at the cutoff date and the event will be censored.
- If a patient has ≥ 2 AE events, the worst grade will be taken into account
- If a patient has ≥ 2 AE events with the same grade, the longest will be taken into account

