3. STATISTICAL METHODS

The analyses outlined in this SAP supersede those specified in the protocol.

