3.5.2 Primary Safety Endpoints

The primary endpoints are the following AE categories:

- Serious AE related to study drug
- Immune-related AE related to study drug

Incidence rates will be provided along with the corresponding 95% Pearson-Clopper CIs. Additionally, both categories will be summarized by SOC, PT and NCI CTCAE grade.

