4. REFERENCES

Kaplan, E. L.; Meier, P. (1958): Nonparametric estimation from incomplete observations. *J. Amer. Statist. Assn.* 53:457–481.

Appendix 1

Protocol Synopsis Version 3

TITLE:	A PHASE III/IV, SINGLE ARM, MULTICENTER STUDY OF ATEZOLIZUMAB (TECENTRIQ) TO INVESTIGATE LONG-TERM SAFETY AND EFFICACY IN PREVIOUSLY-TREATED PATIENTS WITH LOCALLY ADVANCED OR METASTATIC NON-SMALL CELL LUNG CANCER (TAIL)
PROTOCOL NUMBER:	MO39171
VERSION NUMBER:	3
EUDRACT NUMBER:	2017-001409-34
IND NUMBER:	Not applicable
TEST PRODUCT:	Atezolizumab (RO5541267)
PHASE:	Phase III/IV
INDICATION:	Non-small cell lung cancer (NSCLC)
SPONSOR:	F. Hoffmann-La Roche Ltd

Objectives and Endpoints

This study will evaluate the long-term safety and efficacy of atezolizumab in patients with locally advanced or metastatic NSCLC who have progressed following standard systemic chemotherapy (including if given in combination with anti-PD-1 therapy, after anti-PD-1 as monotherapy, or after tyrosine kinase inhibitor [TKI] therapy). Patients with a previously detected sensitizing EGFR mutation or ALK fusion oncogene must have received targeted therapy (TKI) followed by at least one line of standard systemic chemotherapy prior to receiving atezolizumab. Overall, patients should not have received more than two lines of standard systemic chemotherapy. Patients will also be eligible if they discontinued first-line or second-line therapy due to intolerance.

Table 1 Objectives and Corresponding Endpoints

Primary Objective	Corresponding Endpoints
• To evaluate the long-term safety of atezolizumab in previously treated patients with advanced NSCLC	
 • Incidence of serious adverse events (SAEs) related to atezolizumab treatment • Incidence of immune-related adverse events (irAEs) related to atezolizumab treatment
Main Secondary Objective	Corresponding Endpoint

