- Response will be assessed by the investigator using RECIST v1.1 and modified RECIST. Patients who continue atezolizumab treatment beyond radiographic disease progression assessed per RECIST v1.1 will be monitored with a follow-up scan at the next scheduled tumor assessment when the scan frequency is every 6 weeks, and will be assessed by modified RECIST criteria until treatment discontinuation. If the scan frequency is every 9 weeks, a follow-up scan is recommended at 9 weeks or earlier if clinically indicated.
- In those patients for whom tumor assessments are performed as part of local clinical practice and are available for report after PD or atezolizumab treatment discontinuation, best overall response (BOR) and PFS will be assessed from the first date of the new anticancer therapy to the end of the study per RECIST v1.1 and modified RECIST.

The primary objective of the study is to evaluate the long-term safety of atezolizumab. Long-term safety will be assessed by monitoring the nature, severity, duration, frequency and timing of atezolizumab-related SAEs and atezolizumab-related irAEs. An irAE is defined as any adverse event of special interest (AESI) associated with systemic corticosteroid use within 30 days of the onset date. All-causality AEs, all-causality SAEs, AEs and SAEs leading to atezolizumab interruption or discontinuation, and AESIs will also be reported, as well as causes of death, vital signs, physical findings and clinical laboratory results.

Secondary objectives will assess the efficacy of atezolizumab. The main efficacy objective will be to evaluate the OS rate 2 years after the first dose of atezolizumab. Other efficacy objectives will include evaluation of OS, OS rate at 3 years, PFS, ORR, and DOR (additional efficacy assessments may occur on an exploratory basis). All antitumor response assessments will be based on RECIST v1.1 and modified RECIST.

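### SAP 3.5.6 plans no duration summary for atezolizumab-related SAEs and does not limit irAEs to related ones, although Protocol 3.1 names the duration of both in assessing long-term safety

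*SAP*

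**What the plan says.** Protocol 3.1 sets a broad aim: "The primary objective of the study is to evaluate the long-term safety of atezolizumab". The sentence after it, which also stands in the synopsis in SAP Appendix 1 (Description of Study), says how this will be done: "Long-term safety will be assessed by monitoring the nature, severity, duration, frequency and timing of atezolizumab-related SAEs and atezolizumab-related irAEs".

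The endpoints attached to that objective are two incidences: "Incidence of serious adverse events (SAEs) related to atezolizumab treatment" and "Incidence of immune-related adverse events (irAEs) related to atezolizumab treatment". SAP 3.5.2 carries them over as "Serious AE related to study drug" and "Immune-related AE related to study drug".

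Duration is analysed in one place, SAP 3.5.6: "The time to resolution of specific AEs (in months) for AESI and irAE by Category will be analyzed and summarized using Kaplan Meier methodology". The rules that follow start the clock at recorded onset and censor an event without an end date at the data cutoff. From a patient with several events they take the one with the worst grade and, among equal grades, the longest. The section does not mention causality, and SAEs are not among its event sets.

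On precedence, SAP section 3 says: "The analyses outlined in this SAP supersede those specified in the protocol".

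**The concern.** The design section names two event sets and promises a description of how long those events lasted. The one duration analysis in the SAP uses two sets that overlap with these but are not the same. An analyst who follows SAP 3.5.6 to the letter would deliver no duration for a related SAE outside the AESI list, and would deliver irAE curves in which related and unrelated events may be pooled. One attribute by which the trial says it will judge long-term safety would then be missing for one of the named sets and blurred for the other.

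**Working it through.** No sample size, power or event count bears on this point, so the plan has no figure to reproduce. The check is a comparison of sections.

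**1. What each section delivers for the two related sets**

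| Section | Output | Related SAEs | Related irAEs |
|---|---|---|---|
| SAP 3.5.2 | Incidence with exact CI; by SOC, PT and CTCAE grade | Yes | Yes |
| SAP 3.5.4 | Time to first onset | No SAE set | irAEs, no relatedness limit stated |
| SAP 3.5.5 | Incidence of later SAEs and AESIs | Incidence only | Not listed |
| SAP 3.5.6 | Time to resolution | No SAE set | irAEs, no relatedness limit stated |
| Protocol 6.6.1 | Time to first incidence | No duration | No duration |

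Frequency, nature and severity are thus covered for exactly the two related sets. Duration is not, and no other section supplies it.

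**2. Does irAE in SAP 3.5.6 mean related irAE?** The section does not say. Three things suggest that it does not. SAP 3.5.2 writes relatedness out where it is meant. SAP 3.5.3 lists AESIs and treatment-related AESIs as separate outputs, and names related irAEs separately from irAEs. The definition in Protocol 3.1 makes an irAE an AESI with systemic steroid use within 30 days of its start, with no causality condition, and Protocol 5.4 requires AESIs to be reported whatever their cause. The all-cause reading is therefore well supported, but it is inferred from a missing qualifier.

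**3. Can a related SAE fall outside the AESI set?** Yes. The seriousness criteria (Protocol 5.2.2) and the AESI list (Protocol 5.2.3) are independent of each other. Protocol 1.2.2.2 reports pneumonia (2%) and raised AST (2%) as the commonest atezolizumab-related Grade 3 events in an earlier randomised trial. Pneumonia is not on the AESI list (pneumonitis is), and raised AST is listed only above 10 x ULN or as part of potential drug-induced liver injury. Grade 3 is not the same as serious, so this gives no rate. It shows only that important related events can lie outside the list.

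**4. Can the related-irAE duration be recovered from the curve as planned?** Not reliably. Suppose that a patient has a related Grade 2 irAE and an unrelated Grade 3 irAE in the same category. The worst-grade rule selects the unrelated one, and the related one drops out. At equal grades, a longer unrelated event does the same.

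**5. How much could pooling move a median?** This is an illustration in which every input is assumed. Take exponential durations without censoring, a related median of 2.0 months, an unrelated median m between 0.5 and 4 months, and an unrelated share q. The pooled median t solves

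(1 − q)·2^(−t/2) + q·2^(−t/m) = 0.5

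| q | Pooled median, m = 0.5 | Pooled median, m = 4 |
|---|---|---|
| 5% | 1.87 months | 2.06 months |
| 20% | 1.50 months | 2.26 months |
| 50% | 0.93 months | 2.78 months |

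With few unrelated events the missing filter hardly matters; with many it does. The omission of related SAEs outside the AESI list does not depend on q at all.

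**The case against.** The best defence has four parts.

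- **The primary analysis is intact.** Both primary endpoints are incidences, and SAP 3.5.2 analyses them for exactly the related sets. This stands. A reader might infer that duration is itself the primary objective, or that the primary result is at risk. The documents do not support that: the objective is long-term safety, and duration is one of five attributes to be monitored.
- **The event sets overlap heavily.** By definition every related irAE is in the irAE set, and every related SAE that is an AESI is in the AESI set. This also stands. A reader might call 3.5.6 an analysis of the wrong events, but AESI and irAE durations are a legitimate safety summary. The set is incomplete and unfiltered. Containment does not settle the matter, because the selection rule in step 4 can remove the related event.
- **The filter may change little.** Table 11 in Protocol 5.3.4 treats an event as related unless the criteria for a negative answer are met. This narrows the difference between all irAEs and related irAEs by an amount that the documents do not give. It does nothing for the missing SAE set.
- **No protocol analysis was lost.** A reader might infer from the precedence clause that the SAP displaced a duration analysis. It did not: Protocol 6.4 and 6.6.1 contain none, and 3.5.6 adds to them. The mismatch is with the design section and the SAP's own synopsis.

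A practical objection also stands. SAEs include fatal events, which do not resolve, and 3.5.6 has no rule for death before resolution. A filtered rerun alone would not be enough.

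**Conclusion.** The point holds as a gap between the stated assessment of long-term safety and the one planned duration analysis. No section of the SAP gives the duration of atezolizumab-related SAEs as a set, those outside the AESI list get no estimate at all, and SAP 3.5.6 does not confine irAEs to related ones. The statement about SAEs rests on the text alone. The statement about irAEs rests on reading the missing qualifier as all-cause, which the wording of SAP 3.5.2 and 3.5.3 makes likely but does not prove.

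The size is unknown. A count of affected patients is tempting: with assumed related-SAE rates of 5–10% and an assumed non-AESI share of 30–60%, 600 patients would give 600 × 0.05 × 0.30 = 9 to 600 × 0.10 × 0.60 = 36. Neither rate comes from the documents, so that range should carry no weight.

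Nor should a reader conclude that the trial could not report these durations. Protocol 5.3 has seriousness and causality recorded for every event. Protocol 5.5.1 has resolution dates documented and asks sites to try to follow related SAEs to a final outcome. What is missing is the prespecified summary.

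**What to change.** In SAP 3.5.6:

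- Add time-to-resolution summaries for atezolizumab-related SAEs, and for atezolizumab-related irAEs overall and by AESI category.
- Apply the worst-grade/longest selection within each related set, after filtering, so that an unrelated event cannot displace a related one.
- State how an event unresolved at death is handled, for example by censoring at death or by treating death as a competing event. As written, an event with no end date is censored at the cutoff, which for a patient who has died could lie after death.
- Keep the AESI and all-irAE curves as supportive output, and say that they are not restricted by causality if that is the intention.

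The cost is a change of SAP wording, filters on causality and seriousness in an existing program, the added rule for death, and a few more outputs. No new data collection is needed. The drawback is that a pooled related-SAE curve combines unlike events, so it should be labelled descriptive and read alongside the breakdown by event type in SAP 3.5.2.
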